13 SAFETY ANALYSIS

Safety analyses will be conducted using the safety population. Subjects will be analyzed based on the treatment received and the stratum they belong to.

No formal inferential statistics will be performed on safety assessments.

Also, treatment-emergent adverse events by SOC and PT table and summary of weight change will be presented by treatment groups for age 6 to 17 years and ≥ 18 years separately.

	STATISTICAL ANALYSIS PLAN, Version 3.0
Protocol Number: ARQ-151-311	Sponsor: Arcutis Biotherapeutics, Inc.

13.1 Adverse Events

Adverse events (AEs) will be coded according to the latest available version of Medical Dictionary for Regulatory Activities (MedDRA) (Version 25.0).

Treatment emergent adverse events (TEAEs) are defined as any AEs with onset on or after the first study drug application. See [Appendix 2](#) for handling of completely or partially missing dates for AEs. In the case where it is not possible to define an AE as treatment emergent or not, the AE will be classified as treatment emergent. All reported TEAEs will be summarized by treatment group.

Overall summary will be presented, which will include the total number of events, and the number and percentage of subjects who experienced TEAE, TEAE by the strongest relationship, TEAE by the maximum severity, treatment-related TEAE by maximum severity, treatment-emergent serious AE (TESAE), treatment-emergent Non-SAE, TEAE leading to study treatment discontinuation, TEAE leading to study discontinuation, TEAE on an application site, and TEAE leading to death.

The number and percentage of subjects who experience TEAE will be summarized by SOC and PT within SOC. In addition, similar table will be presented by treatment groups for age 6 to 17 years and ≥ 18 years separately. Unless otherwise specified, a subject experiencing the same TEAE multiple times will be counted only once for the corresponding PT. Similarly, if a subject experiences multiple TEAEs within the same SOC, the subject will be counted only once for that SOC. TEAEs will be sorted alphabetically by SOC and within each SOC the PT will be presented by descending frequency in the safety analysis set. A treatment-related TEAE is defined as any TEAE that is assessed by the Investigator as likely, probably, or possibly related to study treatment. TEAE that is assessed as unrelated or unlikely will be defined as not treatment-related. If a subject experiences more than one TEAE within different relationship categories within the same SOC/PT, only the worst case (the strongest relationship) will be reported. TEAE with an unknown relationship will be considered as treatment-related.

The number and percentage of subjects who experience TEAE will be summarized by SOC, PT and the maximum severity (mild/moderate/severe/life threatening/death related to AE). If a subject experiences more than one TEAE within different severity categories within the same SOC/PT, only the worst case (the maximum severity) will be reported. TEAE with an unknown severity will be considered as severe.

The number and percentage of subjects who had TESAE, treatment-emergent Non-SAE, will be summarized by SOC and PT within SOC.

	STATISTICAL ANALYSIS PLAN, Version 3.0
Protocol Number: ARQ-151-311	Sponsor: Arcutis Biotherapeutics, Inc.

Frequency and percentage of subjects who experience TEAE on an application site will be summarized by SOC and PT.

A table and plot of most frequent TEAE (' $\geq 1\%$) by PT will be provided by treatment arms (overall TEAE, overall TESAE will be included in the same plot).

All the AEs will be listed. Any TEAE leading to death will also be included in the AE listing (if there is any). The TEAE related to application site will be flagged in the AE listing.

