- 23. Current or a history of cancer within 5 years with the exception of fully treated skin basal cell carcinoma, cutaneous squamous cell carcinoma or carcinoma in situ of the cervix.
- 24. Parent(s)/legal guardian(s) who are unable to communicate, read, or understand the local language(s). Subjects who are unable to communicate, read or understand the local language, or who display another condition, which in the Investigator's opinion, makes them unsuitable for clinical study participation.
- 25. Subjects who are family members of the clinical study site, clinical study staff, or sponsor, or family members of enrolled subjects living in the same house.

Key Assessments:

Safety Assessments

• Safety will be monitored through local tolerability assessments, vital signs, physical examination, safety labs, Children's Depression Inventory 2 (CDI-2, parent report for children 6-11 years old, inclusive), modified PHQ-A (for adolescents 12-17 years old, inclusive), PHQ-8 (for adults),

C-SSRS (for adolescents and adults 12 years old and older), and AEs.

- After obtaining consent, all AEs and TEAEs should be collected.
- The investigator or a properly trained and designated subinvestigator will perform local tolerability assessments at Baseline/Day 1, and weeks 1, 2, and 4 (Days 8, 15, and 29). Subjects will have vital signs measured at each study visit. Height will be collected at Visit 1(Screening) only.
- A limited physical exam (skin, lungs, and heart only) will be performed at Screening, Baseline/Day 1 and Week 4/Day 29. Blood and urine samples for routine safety laboratory tests (hematology, serum chemistry, and urinalysis) will be obtained at Screening, Baseline/Day 1 and Week 4/Day 29. For all female subjects of childbearing potential, a urine pregnancy test will be administered at all clinic visits except for Screening where a serum pregnancy test will be performed. A negative pregnancy result is required for continued participation in the study, and results (of the urine pregnancy test) must be available prior to dispensing of study drug at study visits.

Efficacy Assessments

• Efficacy assessments will include vIGA-AD (Appendix 2), EASI, WI-NRS, BSA (Appendix 1), DLQI/CDLQI (Appendix 8 and 9), DFI (Appendix 10), SCORAD (Appendix 4), and POEM (Appendix 6).

Pharmacokinetic Assessment

• A single PK assessment (trough) will be performed in all subjects with a blood sample collected at Week 4/Day 29.

Study Endpoints

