- r All AEs should be collected starting after the first application of the investigational product through the end of the study. All SAEs should be collected starting after the signing of the informed consent through 30 days after the last day of the application of the investigational product or the end of the study (whichever is later). Any AEs (whether serious or non-serious) and clinically abnormal laboratory test values(s) will be evaluated by the PI and treated and/or followed up for up to 30 days after end of treatment or until symptoms or value(s) return to normal, or acceptable level, as judged by the PI
- s Subjects who enroll into the open label extension study (ARQ-151-313) must complete the ARQ-151-311 visit requirements at Week 4.

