5.7. Adverse Events

5.7.1. Adverse Event Definition

An AE is defined as any untoward medical occurrence associated with the use of a drug in humans, whether or not considered drug related. An AE can therefore be any unfavorable and unintended sign (including an abnormal laboratory finding), symptom, or disease temporally associated with the use of a medicinal (investigational) product, whether or not related to the medicinal (investigational) product.

A treatment emergent adverse event (TEAE) is defined as an AE that started post application of study medication at the Baseline visit or was present at treatment initiation but worsened during treatment, through study completion.

The definition of AEs includes worsening of a pre-existing medical condition. Worsening indicates that the pre-existing medical condition has increased in severity, frequency, and/or duration or has an association with a worse outcome. When recording such events, provide descriptions that the pre-existing condition has changed (eg,worsening hypertension for a subject with pre-existing hypertension). A pre-existing condition that has not worsened during the study or involves an intervention, such as elective cosmetic surgery or a medical procedure while on study, is not considered an AE.

Progression of treatment indication including new or worsening of anticipated clinical signs or symptoms, which are collected as clinical efficacy variables and assessed as unequivocally associated with the disease progression and /or lack of efficacy, should NOT be reported as adverse events unless the disease progression is greater than anticipated in the natural course of the disease.

In general, abnormal laboratory findings without clinical significance (based on the investigator's judgment) are not to be recorded as AEs. However, abnormal laboratory findings that result in new or worsening clinical sequelae, or that require therapy or adjustment in current therapy, are considered AEs. Where applicable, clinical sequelae (not the laboratory abnormality) are to be recorded as the AE.

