6.8. Adverse Events

All TEAEs occurring during the study will be recorded and classified on the basis of MedDRA terminology for the safety population. TEAEs are defined as those AEs with an onset on or after the time of first study drug application. All reported TEAEs will be summarized by treatment group.

Descriptive statistics will be calculated for quantitative safety data and frequency counts will be compiled for classification of qualitative safety data.

Adverse Events:

The subject incidence of treatment-emergent adverse events (TEAE) will be summarized overall, by severity, and by attribution.

Clinical Laboratory Results:

Shifts in clinical laboratory parameters from baseline to worst post-baseline grade will be provided.

Vital Signs:

The subject incidence of >5% weight loss or gain on study will be provided, as well as whether weight loss was explained or unexplained.

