- Missing day and month: Impute to January 1st, unless year is the same as year of first study treatment dose date then impute to the first study treatment date.
- Missing day: Impute to the 1st day of the month, unless month and year are the same as month and year of first study treatment dose date then impute to the first study treatment date.
- If imputed event start date is after event end date (imputed or not), set the event start date to the imputed event end date.

Event Start Time Imputation (for Adverse Events only)

Imputation of event end time should be done before imputation of event start date.

- If the event date is not the same as the first dose date or time part of the first dose date is missing, impute to 00:00.
- If the event date is the same as the first dose date and event occurred prior to study drug application (as flagged in CRF), impute to 00:00.
- If the event date is the same as the first dose date and event did not occur prior to study drug application (as flagged in CRF), impute to time part of first dose date.
- If the event start date is equal to event end date and imputed event start time is after event end time (imputed or not), set the event start time to the imputed event end time.

Event End Date Imputation

- Completely missing (and not flagged as “ongoing”): Impute to the last contact date.
- Missing day and month: Impute to December 31st, unless year is the same as last contact date then impute to the last contact date.
- Missing day: Impute to the last day of the month, unless year and month are the same as year and month of last contact date then impute to the last contact date.

Event End Time Imputation (for Adverse Events only)

Impute to 23:59.

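### Protocol 5.7.1 counts worsening of an adverse event already present at first dose as treatment-emergent; protocol 6.8 and SAP 13.1 do not, so such an event is tabulated only if the worsening is entered as a new record

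*SAP*

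**What the plan says.** Three places define a treatment-emergent adverse event (TEAE).

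- Protocol 5.7.1 has two limbs. An event qualifies if it began after the first application, or if it "was present at treatment initiation but worsened during treatment, through study completion".
- Protocol 6.8, the analysis section, has one limb: "TEAEs are defined as those AEs with an onset on or after the time of first study drug application".
- SAP 13.1 also has one limb: "Treatment emergent adverse events (TEAEs) are defined as any AEs with onset on or after the first study drug application".

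SAP section 1 says that changes from the protocol are described in section 3.5. That section covers the tube-weight summary, the per-protocol population and the mITT population, and is silent on the TEAE definition.

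The documents disagree on when event collection begins. The protocol synopsis says: "After obtaining consent, all AEs and TEAEs should be collected". Protocol 5.1.1 lists adverse events among the items collected at Screening. Footnote r of the schedule in protocol 1.3 says instead "All AEs should be collected starting after the first application of the investigational product through the end of the study", and sets an earlier start for serious events: "All SAEs should be collected starting after the signing of the informed consent". Protocol 5.1.12, protocol 5.7.5 and the SAP's own schedule agree with footnote r.

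On worsening, protocol 5.7.1 also says: "The definition of AEs includes worsening of a pre-existing medical condition". It asks for a description showing that the condition has changed. It does not say whether that means a new record with its own start date.

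**The concern.** Every adverse event summary in SAP 13.1 is a TEAE summary: overall, by system organ class and preferred term, by relationship, by severity, serious events, events leading to discontinuation or death, application-site events, and the table and plot of frequent terms. The definition therefore decides what is counted anywhere.

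Under 5.7.1 an event that began before dosing and became worse on drug belongs in those tables. Under SAP 13.1 it does not, if its record keeps the earlier start date. Protocol 2.3.7 names diarrhea, nausea, insomnia, depression and anxiety among the events seen with oral roflumilast, and such symptoms can precede dosing and then worsen. If the drug causes some of the worsening, the omission falls more heavily on the active arm. Because the recording rule is open, two identical courses can be counted at one site and left out at another.

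**Working it through.** The plan states no figure on this point, so the check is to follow each type of record through the rules.

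**Step 1. Which records are affected under SAP 13.1**

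| How the event is recorded | Protocol 5.7.1 | SAP 13.1 |
|---|---|---|
| Starts after first application | TEAE | TEAE |
| Starts before first application, worsens on treatment, kept as one record with the early start date | TEAE | Not a TEAE; listing only |
| Worsening entered as a new record dated at the worsening | TEAE | TEAE |
| Start date wholly missing | Depends on the facts | Imputed to first treatment date, so a TEAE, unless an earlier end date pulls it back |

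The definitions give different answers in the second row.

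**Step 2. Whether another rule rescues the second row**

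- SAP 13.1 treats an event as treatment-emergent when its status cannot be determined. A known start date before dosing is determinable, so this default does not apply.
- The imputation in SAP Appendix 2 acts on missing or partial dates and start times. It does not move a known date.
- Protocol 5.7.5 grades each event by maximum severity. One record can therefore carry its on-treatment peak grade under a pre-dose start date. No dated history of severity is described from which a program could detect the worsening.

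**Step 3. Whether such records can exist**

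- Serious events: yes, since they are collected from consent.
- Non-serious events: possible under the synopsis and protocol 5.1.1, but outside collection under footnote r, 5.1.12, 5.7.5 and the SAP schedule.
- Appendix 2 of the SAP provides for the case where the "event occurred prior to study drug application (as flagged in CRF"), so some pre-dose records are foreseen. That rule applies only when the event date is the first-dose date. It is not evidence that events are collected throughout the screening period of up to 30 days.

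**Step 4. Order of magnitude, on assumed rates only**

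Neither rate below is in the documents. Suppose 2% to 5% of 650 subjects have a recorded event ongoing at first dose, and 5% to 20% of those worsen.

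- Low: 650 × 0.02 × 0.05 = 0.65 subjects
- High: 650 × 0.05 × 0.20 = 6.5 subjects
- Active arm share at 2:1 randomization (× 2/3): about 0.4 to 4.3 subjects, over all preferred terms

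If footnote r governs, the first rate is near zero apart from serious events, and the result falls below this range. For comparison, the 1% cut for the frequent-TEAE table needs 5 subjects with a single term in an active arm of about 433 (650 × 2/3 = 433; 1% of 433 = 4.3).

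**The case against.** The strongest reply has four parts.

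- **The SAP follows the protocol's own analysis section.** This stands. A reader might infer that the SAP on its own narrowed a settled protocol definition. The documents do not support that: protocol 6.8 already has the one-limb rule. The silence of SAP 3.5 is also not conclusive. The SAP is based on Amendment 4 of 28 September 2022, while the protocol supplied is the original of 19 October 2020. The two versions do differ: SAP 3.5 cites protocol text on a per-protocol population that section 6.3 of the supplied protocol lacks.
- **Few non-serious events before dosing should be in the database.** This largely stands. A reader might infer that screening-period events are routinely captured. Four places say that non-serious collection starts only after first application, and the Screening and Baseline marks in the schedule carry that footnote, so serious-event collection can explain them. The synopsis and protocol 5.1.1 say otherwise, and the conflict is unresolved.
- **A worsening can be an event in its own right.** This stands in part. If it is entered as a new record it is tabulated, so it would be wrong to infer that worsening never reaches a TEAE table. But nothing tells sites to open a new record.
- **Other outputs would show a signal.** All events are listed. PHQ and CDI-2 category shifts, C-SSRS responses and weight change above 5% are tabulated regardless of TEAE status. This helps for mood, suicidality and weight. It does not help for nausea, diarrhea or insomnia as reported events, and a listing gives no comparison by arm.

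None of this removes the contradiction between 5.7.1 and the rule that generates the tables.

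**Conclusion.** The point holds as an inconsistency in the definition behind all adverse event summaries. For an event with a recorded pre-dose start, kept as a single record, that worsens on treatment, SAP 13.1 gives the opposite answer to protocol 5.7.1 and no other rule corrects it. This covers serious events from consent and any non-serious event recorded at Screening.

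The number affected cannot be derived from the documents and is probably small. The range of about 1 to 7 subjects rests wholly on assumed rates and covers both arms and all terms. A reader might infer that preferred terms will drop out of the 1% table. That would require a term sitting at the cut and the losses falling on it, and nothing in the documents makes this likely. The case for action is consistency of definition, not the count.

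The conclusion assumes that Amendment 4 left the wording of 5.7.1 and 6.8 in place on this point, which has to be checked.

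**What to change.** 1. Check the TEAE wording in Amendment 4. Then use the two-limb definition of 5.7.1 in protocol 6.8 and SAP 13.1: an event that begins at or after first application, or one that began earlier and became worse afterwards.
2. State how the second limb is implemented. As no dated severity history is described, it cannot be assumed that a program can derive it. Either have sites enter a worsening after first application as a new record whose start date is the date of worsening, or count as a TEAE any event with a pre-dose start that is flagged as worsened after first application. For data already collected, the flag could be set by blinded review before database lock.
3. Reconcile the start of event collection: the synopsis and protocol 5.1.1 on one side; schedule footnote r, protocol 5.1.12, protocol 5.7.5 and the SAP schedule on the other.

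The cost is a sentence in each document, one derivation rule, and a short site or eCRF instruction. TEAE counts may rise slightly. No efficacy analysis is touched.

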13.2 Clinical Laboratory

Descriptive statistics for the observed values in chemistry, hematology, and quantitative urinalysis, change from baseline and percent change from baseline values will be presented by treatment group at each scheduled visit. For qualitative urinalysis data, the number and percentage of the subjects for each level of result by treatment at each scheduled visit will be provided.

Shift tables from baseline to each postbaseline assessments describing shifts to out-of-normal range will be provided for chemistry, hematology, and qualitative urinalysis. Only subjects with a baseline result and a result at the specified visit for the parameter will be considered.

Listings of abnormal laboratory will be provided for each parameter where a subject had at least one abnormal result.

Laboratory data will be presented in SI units.

